Based on the literature and our own experience we estimated an approximate occlusion rate of 20% with the standard treatment (saline + heparinized saline flush as described above). The power analysis conducted by [name] determined that, using a two-group normal approximation test of proportions with a one-sided .05 significance level, a sample size of 198 participants per group will have 80% power to reject the null hypothesis that the proposed method is not inferior (i.e. the difference in proportions between the proposed method and the standard method is greater than 0.10). Thus, we will continue data collection until 198 have been completed in each group for a total of 396 study participants who completed 6 months of data collection. To date (July 3, 2019), 69.7% of patients enrolled in the study are able to complete 6 months of data collection without withdrawing for an exclusion criterion (ex: transferring to hospice, being started on an anticoagulant, etc). Therefore, we plan to consent 575 patients to result in 396 who complete the study. Once 396 patients have completed 6 months of data collection will stop and any remaining active participants will be withdrawn from the study.

Data Collection:

Independent Variables: Method for flushing implanted port catheters:

• 20 mL of saline followed by 5 mL of Heparinized saline in a concentration of 100 units/mL

OR

• 20 mL of saline only

Dependent Variables:

Primary Outcomes

- Occurrence of first complete (can neither withdraw blood nor flush the catheter) occlusion
- Occurrence of first partial (able to flush but unable to withdraw blood) occlusion
- Frequency with which alteplase (CathFlo) has to be utilized to resolve an occlusion

Secondary Outcomes

- Number of subsequent occurrences of complete or partial occlusions after the first occurrence.
- Amount of time in days that a port remains patent (flushes easily and able to obtain a blood return).
 - Amount of time between entrance in study and first incidence of partial or complete occlusion
 - Amount of time between incidences of partial or complete occlusion.
- Occurrence of other complications:
 - Central Line-Associated Blood Stream Infection (CLABSI) a laboratory-confirmed (recognized pathogen cultured from one or more blood cultures; organism cultured from blood is not related to an infection at another site) blood stream infection that is considered central line associated (CDC, 2012).
 - Develops complication related to Heparin

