Participants in the control group will have their implanted port catheters flushed according to the established site's policy. Following the use of the port catheter with no continuous fluids running, or before de-accessing a port catheter (removing the port needle), the port will be flushed with 20 ml of normal saline and 5 ml of heparinized saline in the concentration of 100 units of heparin per ml.

Participants in the intervention group will have their ports flushed with normal saline only. That is, following the use of the port catheter with no continuous fluids running, or before de-accessing a port catheter (removing the port needle), the port will be flushed with 20 ml of normal saline. Turbulent flushing technique (the solution is injected using a push/pause technique every 1 mL) will be used in both groups and all accessed port catheters will have a neutral displacement connector. The MicroCLAVE[®] Clear displacement connector (ICU Medical, Inc., San Clemente, CA, USA) is the current product in use. Participants in both groups will be seen in a TriHealth Cancer Institute Infusion Center or the UCMC Barrett Infusion Center at a frequency consistent with their individual treatment plan and as outlined in the site's policy. Participants will remain in the study for 6 months or until they experience one of the potential risks noted below. Participants will be considered as having completed the study if they participate for 6 months.

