Potential risks for study participants in either arm of the study include partial occlusion (can instill flush solution but not withdraw blood) and complete occlusion (can neither instill flush solution nor withdraw blood). Study participants could require removal of the port if an occlusion cannot be resolved, and possibly require re-insertion of a new implanted port. In the event of any occlusion, alteplase (CathFlo) in the policy established dose and frequency (see Appendix A) will be instilled to resolve the occlusion. Study participants whose implanted ports are found occluded on three (3) consecutive visits to the treatment center will be excluded from further data collection, i.e., their participation in the study will be terminated. The standard flushing as prescribed by the site's policy or as prescribed by the attending physician will be used. Study participants whose occlusion cannot be resolved with alteplase and require removal of the port will also be terminated and excluded from further data collection. Patients who develop port infections necessitating port removal will be terminated and excluded from further data collection. Study participants who develop HIT (heparin induced thrombocytopenia) or other heparin allergy will be terminated and excluded from further data collection. Likewise, patients who have thrombotic or embolic phenomenon requiring therapeutic anticoagulation will be terminated and excluded from further data collection. If a participant in the intervention group receives clinical care and their port is flushed with heparin (following standard hospital policy), the participant will be withdrawn from the study.

The study will be closed if there is evidence that study participants in the intervention arm experience implanted port occlusion at a disproportionate rate. The amount of alteplase (CathFlo) used in each group will be assessed each

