Statistical Analysis: Descriptive statistics will be used to describe the participants. Differences between groups on the dependent variables will be calculated using t-test, Chi-Square or Fisher's exact test as appropriate for the level of data under analysis (also see discussion regarding interim analysis). Regression analysis will be used to determine the effect of the moderating variables on the occurrence of occlusion in the implanted ports. Participants in the control group and intervention group will be further stratified based on frequency of port flushing. Differences in the rate of occlusion between stratified groups will also be calculated.

Ethical Considerations: The purpose of this study is to determine the safest and most effective flushing solution(s) for maintaining patency in implanted port catheters. In so doing, study participants could be placed at potential risk for catheter occlusion. All catheter occlusion will be treated according to the site's policy, i.e., the instillation of alteplase (CathFlo) (see Appendix A). Potential study participants will be made aware of

the risk when enrolled in the study (See Appendix B (V.2, 2-20-2015) script for recruiting patients into the study and Appendix F, the Informed Consent Statement).

- **Informed Consent:** Patients who meet inclusion criteria will be approached by a member of the research team who will explain the study, implications of their participation and review the Informed Consent Statement and HIPAA Authorization Form(s) (see Appendix F and G). Participants will receive a copy of the signed Informed Consent Statement and HIPAA Authorization. The original signed Informed Consent Statement and HIPAA will be stored in a locked cabinet at a TriHealth office or locked location at UCMC, or an off-site locked storage area, for six years after the study is closed at which time the documents will be destroyed via mechanical shredder.

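### Alteplase frequency, a primary outcome, and the monthly alteplase check have no follow-up denominator, although about 30% of participants leave before 6 months

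*Combined protocol and SAP*

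**What the plan says.** Under Dependent Variables, one of three primary outcomes is "Frequency with which alteplase (CathFlo) has to be utilized to resolve an occlusion". No unit (doses, treated visits or treated participants), time base or denominator follows.

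Statistical Analysis gives one rule for all outcomes: "Differences between groups on the dependent variables will be calculated using t-test, Chi-Square or Fisher's exact test as appropriate", according to the level of the data. The regression in that section concerns the occurrence of occlusion, and the stratification is by flushing frequency. Neither adjusts alteplase use for length of follow-up.

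Experimental Aspect of the Study adds a monthly check: "The amount of alteplase (CathFlo) used in each group will be assessed each" month. No number at risk, participant-time or threshold is attached.

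Follow-up is not the same for everyone. "Participants will remain in the study for 6 months or until they experience one of the potential risks noted below". The sample-size text under Recruitment reports that "69.7% of patients enrolled in the study are able to complete 6 months of data collection without withdrawing for an exclusion criterion", and concludes "we plan to consent 575 patients to result in 396 who complete the study". Three further rules shorten follow-up:

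- Alteplase on three consecutive visits ends participation in either arm (Data collection tool).
- A heparin flush given during other clinical care withdraws a participant only in the saline arm (Experimental Aspect of the Study).
- Anyone still active when 396 have completed is withdrawn (Recruitment).

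**The concern.** The number of alteplase uses grows with time under observation. A t-test on that number divides by participants but not by how long each was watched; a chi-square or Fisher's exact test on any use has the same limitation. A monthly total per group depends also on how many participants are active in each arm that month.

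If the arms are followed for different lengths of time, the one followed for less appears to need less alteplase at the same true rate. The documents give a reason for unequal follow-up in each direction. Withdrawal after a heparin flush shortens saline follow-up and would make saline look better. Termination for heparin-induced thrombocytopenia (HIT) or heparin allergy would fall mainly on the heparin arm and act the other way. What is at stake is the interpretation of a listed primary outcome and of a monthly monitoring figure.

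**Working it through.** **Inputs from the protocol.** Completion 69.7%, both arms together; 575 to be consented for 396 completers; 198 completers per group; control occlusion rate 20%; margin 0.10; one-sided alpha 0.05; power 80% (all Recruitment). For illustration: 134 alteplase doses in about a year (Care of Implanted Port Catheters at TriHealth) and 70 treated patients in FY 2012 (Recruitment).

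**The plan's own figures.** n = (1.645 + 0.842)² × 2 × 0.20 × 0.80 / 0.10² = 197.9, so 198 per group, as stated. Dropout: 396 / 0.697 = 568.1, so 569 against 575 planned, which is close. Early leavers: 575 × 0.303 = about 174. These figures concern occlusion; no sample size or power is given for alteplase use.

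**Size of the possible bias.** Assume equal true rates in the arms and leaving spread uniformly over 6 months. With completion share c, mean follow-up as a fraction of 6 months is c + 0.5(1 − c). The ratio of counts per participant, saline to heparin, then equals the ratio of mean follow-up. The splits by arm are assumptions centred on 69.7%.

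| Completion, saline / heparin | Mean follow-up | Ratio |
|---|---|---|
| 69.7% / 69.7% | 0.8485 / 0.8485 | 1.00 |
| 68% / 71.4% | 0.840 / 0.857 | 0.980 |
| 65% / 74.4% | 0.825 / 0.872 | 0.946 |
| 60% / 79.4% | 0.800 / 0.897 | 0.892 |

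So the saline rate is understated by about 2%, 5% and 11%. In the middle case a true rate ratio of 1.5 would read as 1.5 × 0.946 = 1.42. If the gap ran the other way, the heparin rate would be understated instead. With participant-time as denominator the ratio is 1.00 in every row.

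**Sensitivity to timing.** If all leavers go at month 1, a 10-point gap gives 0.89 and a 20-point gap 0.80. If they go at month 5, a 20-point gap gives 0.97. Equal completion with saline leavers going at month 2 and heparin leavers at month 4 gives (0.697 × 6 + 0.303 × 2) / (0.697 × 6 + 0.303 × 4) = 4.79 / 5.39 = 0.89.

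**Effect on detection.** About 287 are enrolled per arm (575 / 2). Assume a mean of 0.20 × 134 / 70 = 0.383 uses per participant over 6 months, and negative binomial counts with k = 0.224, which leaves (0.224 / 0.607)^0.224 = 0.80 with none, so 20% affected. This mean is an assumption: the 134 doses cover all central lines, the 70 patients are port patients from a slightly different period, and both are yearly figures. In simulation at 65% / 74% completion, with a two-sided 0.05 test counted in the harm direction:

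| True rate ratio | t-test of counts | Rate comparison |
|---|---|---|
| 1.5 | about 32% | 42–44% |
| 2 | 80–81% | 88–90% |

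If instead only 198 completers per arm were analysed, the two methods nearly agree: about 33% against 35%, and 77% against 80%.

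**The case against.** The protocol nowhere says that raw counts will be compared. Frequency can mean a rate, and the tests are to be chosen to suit the data. This stands: what can be said is that no denominator is specified and that none of the named tests uses exposure time.

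The sample size counts completers. If only completers were analysed, everyone would have 6 months and the final comparison would not suffer from unequal follow-up. That also stands, but the analysis set is not defined, and such an analysis would drop participants terminated for repeated alteplase use. The monthly check would still lack a denominator.

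A reader might infer that the plan favours saline. The documents do not support this. Completion by arm is not reported. The saline-only withdrawal rule points that way, but termination for HIT or heparin allergy points the other way, and the background section puts HIT at 1–5% of exposed patients. How often a stray heparin flush occurs is not stated.

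A reader might also infer that the safety stopping rule is compromised. It is not shown to be: the interim analyses that can close the study use first partial plus first complete occlusion, and no threshold is attached to the alteplase check.

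Finally, an offset does not cure everything. Follow-up can end because of alteplase use itself, and such censoring is informative.

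**Conclusion.** The point holds as a gap in definition and method that should be closed before the final analysis. A primary outcome and a monthly monitoring figure have no follow-up denominator in a trial where 30.3% leave early. The resulting bias is possible, not demonstrated, and vanishes with equal retention and timing. Under the assumed gaps of about 3, 9 and 19 points with uniform leaving it is about 2%, 5% and 11%. It could be larger with very early leaving, and the largest gap has no support in the documents beyond being possible. The loss of power shown depends on the assumed mean, the assumed dispersion, the 65% / 74% split and analysis of everyone enrolled. The non-inferiority hypothesis on occlusion and the 198 per group do not change.

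**What to change.** - **Outcome:** define it as alteplase uses per participant-time on study, stating whether a use is a dose or a treated visit.
- **Analysis:** include all randomised participants in a negative binomial (or quasi-Poisson) regression with arm as factor and log follow-up days as offset. Report the rate ratio with its confidence interval.
- **Sensitivity:** repeat the analysis per port access, because alteplase is given at visits and visit frequency follows each participant's treatment plan.
- **Follow-up:** report time on study and reasons for leaving by arm, showing separately those terminated after alteplase on three consecutive visits, since the offset does not remove that dependence on the outcome.
- **Monthly check:** tabulate doses and participants treated by arm, beside participants at risk and participant-days.

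The cost is analysis-plan wording, a standard model and extra columns in the monthly table. Visit dates and alteplase doses are already entered on the Record of Flushes, so no new data or participants are needed. The small downside is that the result is a rate ratio rather than a difference in means.

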When the potential study participant arrives in the treatment center, a member of the research team will escort the patient into a treatment room and explain the study by reading a prepared script (see Appendix B). If the patient expresses interest, the Informed Consent Statement and HIPAA Authorization form will be reviewed and signed. After obtaining informed consent, a participant will be randomly assigned to the heparinized saline flush (control group) or saline only flush study group (intervention group). A color-coded sticker will be placed on the patient's treatment folder indicating participation in the study and group assignment. The random assignment process will be achieved using sequentially-numbered opaque sealed envelopes (SNOSE) containing the group assignment. A yellow colored data collection face sheet (see Appendix C) will indicate control group; a blue colored data collection face sheet will indicate the intervention group.

During FY 2012, 391 patients with implanted port catheters were treated in the OPCC. Seventy of these patients experienced an occlusion of their port that required the administration of alteplase (CathFlo) ([name], personal communication, October 12, 2012). Thus, 70 of 391 experienced an occlusion resulting in an occlusion rate of 18%. Some of these 70 patients experienced an occlusion more than once during that time. Additionally, during that time, a few patients had their implanted port catheters removed due to infection or malfunction. The exact number of patients who experienced multiple occlusions or had their implanted ports removed/replaced during FY2012 is unknown.

We engaged the consultation of a biostatistician through the Center for Clinical and Translational Science and Training (CCTST) to conduct a power analysis to establish the number of participants needed in each group to determine the non-inferiority of the alternative therapy (saline only flush). Consultation was provided by [name], Associate [name] Hospital Medical Center, University of Cincinnati.

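### Subsequent occlusions and time between occlusions are compared between arms with no stated denominator or allowance for time at risk; a comparison among occluders only can be biased in either direction

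*Combined protocol and SAP*

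**What the plan says.** Under Dependent Variables, Secondary Outcomes, the protocol lists the "Number of subsequent occurrences of complete or partial occlusions after the first occurrence" and, within the patency-time outcomes, the "Amount of time between incidences of partial or complete occlusion". First complete and first partial occlusion are primary outcomes in the same list, as is how often alteplase is needed.

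The Statistical Analysis section gives one rule for all of these: "Differences between groups on the dependent variables will be calculated using t-test, Chi-Square or Fisher's exact test as appropriate" for the level of data. It names no analysis set for the secondary outcomes, no value for a participant who never occludes, and no rate or recurrent-event model.

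Follow-up lasts up to six months but can end early. Under Data collection tool and Experimental Aspect of the Study, participation stops after alteplase or occlusion at three consecutive visits, and after port removal for an unresolved occlusion.

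On how often occlusions recur, the Recruitment section says: "The exact number of patients who experienced multiple occlusions or had their implanted ports removed/replaced during FY2012 is unknown".

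**The concern.** A gap between occlusions needs a first occlusion. A count that starts after the first occlusion is most naturally read in the same way. If the arms are compared among occluders, the two sets are selected after randomisation by the event that the flush solution may change. A difference between them then mixes any effect on recurrence with a difference in who entered each set.

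Two further problems apply:

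- **Time at risk.** A port that first occludes in month five has about one month left in which to recur; one that occludes in week one has most of six months. A t-test on raw counts ignores this.
- **Truncation.** The termination rules cut the count short in the ports that occlude most.

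At stake is the recurrence part of the second research question, on the type and rate of complications. An occluder-only result could be read as evidence about saline when it largely reflects selection.

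**Working it through.** **The plan's own figure.** The sample size is stated "using a two-group normal approximation test of proportions with a one-sided .05 significance level", and "a sample size of 198 participants per group will have 80% power to reject the null hypothesis". With 20% in both arms and a margin of 0.10:

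n = (1.645 + 0.842)² × (0.20×0.80 + 0.20×0.80) / 0.10² = 6.18 × 0.32 / 0.01 ≈ 198 per group.

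This reproduces exactly, and it concerns first occlusion only. The plan gives no figure for recurrence.

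**Inputs for the illustration**

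- Heparin arm: 20% occlude ("we estimated an approximate occlusion rate of 20% with the standard treatment").
- Saline at the margin: 20% + 10 points = 30%.
- Occluders available: 198 × 0.20 ≈ 40 on heparin; 198 × 0.30 ≈ 59 on saline at the margin.
- Recurrence (assumption): 134 alteplase doses (Care of Implanted Port Catheters at TriHealth) / 70 patients (Recruitment) = 1.914 events per occluder, so 0.914 later events. This is a rough proxy.
- Heparin total: 0.20 × 1.914 = 0.383 occlusions per participant.

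**Formulas.** With N the number of occlusions per participant:

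- later occlusions per occluder = E[N] / P(N≥1) − 1
- later occlusions per randomised participant = E[N] − P(N≥1)

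**Three ways saline could be worse**

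- A. Saline adds 10 points of ports that occlude once only. Total = 0.383 + 0.10 = 0.483; per occluder = 0.483/0.30 − 1 = 0.61.
- B. The extra occluders recur like the others. Total = 0.30 × 1.914 = 0.574; per occluder = 0.914.
- C. Saline multiplies every port's rate by 1.5 (negative binomial). The heparin figures require (1 + 0.383/k)^(−k) = 0.80, giving k = 0.224. Saline total = 1.5 × 0.383 = 0.574; P(N≥1) = 1 − (1 + 0.574/0.224)^(−0.224) = 0.248; per occluder = 0.574/0.248 − 1 ≈ 1.32.

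| | Heparin | Saline A | Saline B | Saline C |
|---|---|---|---|---|
| Any occlusion | 0.20 | 0.30 | 0.30 | 0.248 |
| Later occlusions per occluder | 0.91 | 0.61 | 0.91 | 1.32 |
| Later occlusions per randomised participant | 0.18 | 0.18 | 0.27 | 0.33 |
| Total occlusions per randomised participant | 0.38 | 0.48 | 0.57 | 0.57 |

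Saline is worse in A, B and C. The occluder-only row shows it as better, equal and worse respectively; the total row shows the excess each time.

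**Sensitivity to assumed recurrence.** In A, heparin means of 0.5 and 1.5 give 0.50 v 0.33 and 1.50 v 1.00 (heparin v saline). For a proportional increase from 20% to 30% occluding, a Poisson model gives 0.12 v 0.19, and gamma frailty gives 0.25 v 0.43 (shape 1) and 0.41 v 0.74 (shape 0.5). The direction depends on the mechanism, not on the recurrence level.

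**Simulation, 198 per arm, full follow-up, no early termination**

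- In A, the occluder-only mean is lower on saline in about 85% of trials, and significantly lower in 16% to 20% across runs and forms of t-test.
- In A with zeros for participants who never occlude, saline is falsely favoured in about 2.5% of trials, the nominal rate.
- In C, power is 16% to 19% for the occluder-only t-test and 33% to 35% for a t-test of totals.

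**The case against.** The strongest reply is that the plan never restricts the count to occluders. It compares the randomised groups, and a port that never occluded can score zero. On that reading everyone is in the comparison and the selection problem disappears for the count. This stands. A reader might infer that the outcome exists only for occluders, so that its comparison cannot be a randomised one; the documents do not support that for the count. They leave the denominator open, so it could be chosen after the data are seen. For the gap time, the restriction is unavoidable.

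A reader might also infer that saline would look better because it causes more first occlusions. That is not general. It needs the extra saline occluders to recur less than the others, which nothing in the documents establishes. Under a proportional increase the occluder-only comparison goes against saline.

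Third, alteplase frequency is already a primary outcome and captures much of the total burden. This stands in part. The Data collection tool section also gives alteplase for sluggish withdrawal, which falls short of the partial-occlusion definition, and the denominator and model for that outcome are no better specified.

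Finally, the recurrence input is weak. Doses are not occlusions, line type was not summarised for the 134 doses, the two reporting periods may not coincide, and roughly yearly figures are applied to six months. The simulation also omits the termination rules, which would remove some high counts. All of this stands; the numbers illustrate direction and are not forecasts.

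**Conclusion.** The concern holds for two secondary outcomes. The gap-time comparison is necessarily made in sets selected after randomisation. The count comparison is too, unless participants who never occlude are scored zero, which the plan does not say. Neither planned comparison allows for time at risk or early termination.

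The direction of bias is unknown: 0.61 v 0.91 per occluder (saline v heparin) under one mechanism and 1.32 v 0.91 under another, with saline worse in both. These figures rest on a 20% heparin occlusion rate, 1.914 events per occluder from the dose proxy, and the assumed mechanisms.

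It should not be inferred that the trial's main conclusion is at risk. The non-inferiority hypothesis, the 198 per group and the interim rule all rest on first occlusion and are unaffected. In scenario A saline sits at the 10-point margin, where the primary test would correctly fail about 95% of the time. The change is worth making, but it is not critical.

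**What to change.** Make the arm comparison on the total number of partial or complete occlusions per participant, over all randomised participants, with zero for those who never occlude. Analyse it as a rate with follow-up time as offset (negative binomial), or by a recurrent-event model with robust variance.

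State how participants terminated early are handled. Some terminations are triggered by the occlusions themselves, so the offset alone does not settle this.

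Report subsequent occlusions among occluders, and gap times, as description only, with no test between arms. Read the total beside the first-occlusion analysis and the alteplase-frequency outcome.

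The cost is a few sentences of protocol text and one model. Dates and patency are already recorded at each visit on the Record of Flushes, so no new data are needed. The small downside is that a total mixes first and later occlusions, which is why the first-occlusion result must sit beside it.
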